5.4. Endpoints

5.4.1. Efficacy Endpoints

Migraine and headache endpoints are defined in [Table CGAP. 4.2](#). Each month is defined as a 30-day period with migraine or headache measures normalized from the visit intervals.

Information recorded in the paper diary, the possible responses and the assignment to the type of headache is presented in [Table CGAP. 5.1](#) (EM patients) and [Table CGAP. 5.2](#) (CM patients). The medication will be recorded and the headache information will be summarized for eCRF as shown below. Note that the exception is EM patients at CGAP Visit 3. It will be based on CGAN Visit 12 information, as stated in CGAP Protocol Section 2, Schedule of Activities, footnote [a]. The paper diary collected following information:

During Study Period III:

- Number of diary days completed by the patient since the last visit?
- How many migraine headache days did the subject experience since the last visit?
- How many headache days did the subject experience since the last visit?
- How many days did the subject take any pain medication for migraine or headache since the last visit?
- How many days did the subject take any pain medication for migraine since the last visit?

During Study Period IV for assessment of first 30 days in the 60-day period since last visit:

- Number of diary days completed by the patient during Days 1-30 of the 60-day period since the last visit?
- How many migraine headache days did the subject experience during Days 1-30 of the 60-day period since the last visit?
- How many headache days did the subject experience during Days 1-30 of the 60-day period since the last visit?
- How many days did the subject take any pain medication for migraine or headache during Days 1-30 of the 60-day period since the last visit?
- How many days did the subject take any pain medication for migraine during Days 1-30 of the 60-day period since the last visit?

During Study Period IV for assessment of second 30 days in the 60-day period since last visit:

- Number of diary days completed by the patient during Days 31-60 of the 60-day period since the last visit?

- How many migraine headache days did the subject experience during Days 31-60 of the 60-day period since the last visit?
- How many headache days did the subject experience during Days 31-60 of the 60-day period since the last visit?

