Yesterday, was the headache made worse by your usual daily activity	Yes	Migraine Criteria A
	No	
Q4. Yesterday, did the headache come with sensitivity to light and sound?	Yes	Migraine Criteria B
	No	
Q5. Yesterday, did you feel sick to the stomach or throw-up with the headache?	Yes	Migraine Criteria B
	No	
Q6. Yesterday, did you take any medicine for your headache?	Yes	Medication will only count as headache medication on a day a headache occurred.
	No	
Q7. Do you believe you experienced a migraine AND it was relieved by a triptan or ergot derivative?	Yes	Migraine Criteria C
	No	

Abbreviation: Q = question.

^a If “No” is answered for Q1, then the patients will skip the other questions.

Efficacy Measure: the Number of Monthly Migraine Headache Days

One of the efficacy measures is the number of monthly migraine headache days. A migraine headache day is defined as a calendar day on which a **migraine or probable migraine** occurs.

The number of monthly migraine headache days will be summarized from the daily diary data for each patient in that period (including 30 days of daily data from the baseline period prior to randomization, 12 months of daily data during the treatment phase, and 4 months of daily data during the post-treatment phase).

The daily data will be aggregated, and the number of migraine headache days will be provided for each of the 30-day periods. In calculating the number of migraine headache days for each period, if the period is not equal to 30 days, the number of migraine headache days will be

normalized by multiplying the number of migraine headache days by $(30/x)$ where “x” is the total number of non-missing diary days in the period.

For SP III, Month 1 period data is based on headache information from Visit 3 up to on Visit 5-1 day. Month 2 period data is based on headache information from Visit 5 up to Visit 6 – 1 day. Month 3, to Month 12 will be defined similarly.

For the 4 months of the post-treatment period, the monthly interval will be derived as below. Firstly, the 2-month visit interval (60 days) will be split into two 1-month periods for efficacy measures. Day 1 (the first day of post-treatment period) to Day 30 will be for the first 1-month period and Day 31 to Day 60 for the second 1-month period. Even if diary is recorded longer than 60 days, these will be ignored.

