For patients who discontinued early during the post-treatment phase, if the date of discontinuation is within 30 days of previous visit date, all data between the previous visit date and the discontinuation date will go to 1 monthly period; if the date of discontinuation is more than 30 days of the previous visit date, then the first 30 days will be the first monthly period, and the rest will be considered as part of the second monthly period (up to 60 days).

Example 1: A patient has 64 days between Visit 17 and Visit 18. He completes the study on Visit 18. Then he has:

- 1st half month = diary data from Day 1 to Day 30
- 2nd half month = diary data from Day 31 to Day 60

Example 2: A patient has 44 days between Visit 17 and Visit 18. He discontinues the study on Visit 18 (i.e., disposition is not marked as completed). Then he has:

- 1st half month = diary data from Day 1 to Day 30
- 2nd half month = diary data from Day 31 to Day 44

Additionally, if the compliance rate for each monthly interval is $\leq 50\%$, then all endpoints to be derived from the diary data for that 1-month period will be considered missing. For the post-treatment phase, the derived 1-month periods (resulting from splitting 2-month visit interval) will be treated similarly.

For a patient who discontinued early in the treatment phase, the compliance rate for the last month of that study period will be calculated with the denominator of the maximum of 30 and the total number of calendar days in that month, i.e., $\max(30, \text{the total number of calendar days in that month})$.

For a patient who discontinued early in the post-treatment phase, the compliance rate for the last month of that study period will be calculated with the denominator of 30. (For example, as shown above in Example 1, Visit 17 and Visit 18 can be split into 2 months. Each of them can

have 30 days as maximum duration.) For the rest of months and patients, the compliance rate will be calculated as described in Section 5.5.7.

The Other Efficacy Measures

The same approach to adjusting the number of days within each period to a 30-day period and the same approach to imputing monthly data based on compliance as described above will be applied to all efficacy measures that are derived from diary data and need normalization to 30-day period, including:

- **Number of headache days** is calculated as the number of calendar days in a 30-day period on which a headache occurs.

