5.5.1.2. Handling of Dropouts or Missing Data

No imputation method will be used for a visit if a certain measure at the visit is determined as missing. For example, if the compliance rate for each monthly interval is $\leq 50\%$, then all endpoints to be derived from the diary data for that 1-month period will be considered missing; otherwise, the endpoints at that month (visit) is not missing.

Please refer to Section 5.4.1 for approach to handling missing diary data for derivation of the number of migraine headache days and other efficacy measures.

For MMRM analysis on the repeated measures analyses, the model parameters are simultaneously estimated using restricted likelihood estimation incorporating all of the observed data. Estimates have been shown to be unbiased when the missing data are MAR (missing at random).

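### SAP 5.4.1 triggers the 30/x diary correction on period length but divides by completed entries, so read literally a 30-day period with 16 to 29 entries is left unscaled

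*SAP*

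**What the plan says.** SAP 5.4.1 reports diary measures per 30 days. The correction applies when a condition on the period is met: "if the period is not equal to 30 days, the number of migraine headache days will be" multiplied by 30/x. In that same sentence x "is the total number of non-missing diary days in the period".

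Period lengths are set as follows.
- Treatment months (Study Period III) run from one visit to the day before the next. The target interval in the addendum's Schedule of Activities is 30 days (14 + 16 for Month 1).
- Follow-up months (Study Period IV) are fixed blocks: "Day 1 (the first day of post-treatment period) to Day 30 will be for the first 1-month period", and Days 31 to 60 form the second. SAP 5.5.7 sets 30 expected diary days for each of Months 13 to 16.
- Baseline is described as "including 30 days of daily data from the baseline period prior to randomization" in SAP 5.4.1, but as Visit 2 to Visit 3 for chronic migraine (CM) patients in SAP 5.5.4.

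A month with compliance of 50% or less is set to missing. For patients who leave follow-up early, "the compliance rate for the last month of that study period will be calculated with the denominator of 30".

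The rule reaches beyond migraine days: "The same approach to adjusting the number of days within each period to a 30-day period" is applied to the other diary measures. SAP 5.5.1.2 relies on it for missing entries: "Please refer to Section 5.4.1 for approach to handling missing diary data for derivation of the number of migraine headache days".

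**The concern.** Period length and completed entries are different quantities; SAP 5.5.7 itself divides one by the other to get compliance. A 30-day month with 24 entries does not meet the stated trigger, although x is 24. Taken at its word, the rule counts the six missed days as days without migraine. No other section scales such a month, and SAP 5.5.1.2 excludes any other imputation.

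This is the standard case, because 30 days is the length of every full follow-up month and the target for every treatment month. The output most exposed is time to first loss of 50% response, a secondary endpoint judged on follow-up months among Month 12 responders. Understated counts can hold a patient above the 50% line for longer. The migraine-day MMRM over Study Periods III and IV combined and the six-arm descriptive summaries take the same counts. Two programmers could both follow the SAP and report different values.

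**Working it through.** The plan states no figure on this point, so the rule is applied directly.

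**Inputs.** L is the period length and x the number of completed entries. The literal factor is 1 if L = 30 and 30/x otherwise. The general factor is 30/x for every period.

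**Range affected.** In a 30-day period, 15/30 = 50.0% is set to missing and 16/30 = 53.3% is kept. The two rules therefore differ only at L = 30 with x from 16 to 29.

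**Jump at 30 days (treatment phase).** Take 12 migraine days on 24 entries. At L = 29 or 31 the result is 12 × 30/24 = 15.0. At L = 30 it stays at 12.0.

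**Understatement of the expected count, 1 - x/30, and the true reduction that reads as 50%, 1 - 0.5 × 30/x** (the latter assumes a complete or scaled baseline):

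| Entries x | Understatement | Days lost at a true 10 per 30 | True reduction that reads as 50% |
|---|---|---|---|
| 29 | 3.3% | 0.3 | 48.3% |
| 27 | 10.0% | 1.0 | 44.4% |
| 24 | 20.0% | 2.0 | 37.5% |
| 16 (lowest kept) | 46.7% | 4.7 | 6.25% |

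**Probability that a month is classed as a 50% response.** Assumptions: complete baseline of 20 per 30, independent days, daily probability p = 20 × (1 - reduction)/30. A response is a monthly count of 10 or less. Unscaled, this is P(X ≤ 10) on x entries. Scaled, it is P(X ≤ 10x/30), so the cut-off is 9 at 29 and 27 entries and 8 at 24. With a complete diary it is P(X ≤ 10) on 30.

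| True reduction | Complete diary | 29 entries: unscaled / scaled | 27 entries: unscaled / scaled | 24 entries: unscaled / scaled |
|---|---|---|---|---|
| 40% | 0.291 | 0.343 / 0.215 | 0.458 / 0.309 | 0.650 / 0.328 |
| 50% | 0.585 | 0.636 / 0.483 | 0.734 / 0.589 | 0.860 / 0.594 |
| 60% | 0.849 | 0.876 / 0.775 | 0.921 / 0.842 | 0.966 / 0.835 |
| 70% | 0.974 | 0.980 / 0.951 | 0.989 / 0.970 | 0.996 / 0.964 |

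Scaling is close to the complete diary at 27 and 24 entries, where 10x/30 is a whole number. At 29 entries it is further off than not scaling, because the cut-off drops a whole day for one missed entry.

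**Baseline offset.** If a CM baseline were itself an unscaled 30-day block with 24 entries, an unchanged migraine rate would show an apparent reduction of 1 - 24/24 = 0% with 24 follow-up entries and 1 - 16/24 = 33% with 16.

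**The case against.** The strongest reply is that the SAP already shows its intent. It defines x by completed entries, calls the measures normalized, and names 5.4.1 as the method for missing diary data. The literal reading would leave that pointer with little to do in a full 30-day month, and programming may already scale every period. This stands as evidence of intent, and it is why the point is an internal conflict. It does not fix the derivation, because the condition as printed still excludes 30-day periods.

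The other side is also right that responder classification does not always improve. With one missed entry and a true 50% reduction, scaling gives 0.483 and no scaling 0.636, against 0.585 with a complete diary. Scaling still removes the downward bias in the expected count at every x, if missed days resemble recorded ones.

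A reader might infer more than the documents support:
- **That reported follow-up results are biased.** Nothing shows that the literal rule was programmed, and no missing-entry rate is given. The 16-entry row is a bound, not an expectation. The 80% diary requirement in inclusion criterion 7 covers the CM baseline only.
- **That the CM120 versus CM240 comparison is biased.** It is not, systematically, unless missingness differs by arm.
- **That all arms lean the same way.** About 240 of the 300 patients have episodic migraine (EM). Their baseline is CGAN Month 6 from an electronic diary, and its derivation is not shown.
- **That a follow-up visit one day early causes the same jump.** SAP 5.4.1 fixes the second block at Days 31 to 60, SAP 5.5.7 fixes 30 expected days, and only early discontinuers have a block explicitly shortened. The jump is shown for treatment intervals only.

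**Conclusion.** The point holds as a conflict within one sentence of SAP 5.4.1 that should be corrected. Followed literally, the rule leaves 30-day periods with 16 to 29 entries unscaled and understates their expected count by 1 - x/30, that is 3% at 29 entries, 10% at 27 and 20% at 24. The effect on response status is large near the 50% cut-off and small for strong response: at 24 entries, 0.65 against 0.33 at a true 40% reduction, but 0.996 against 0.964 at 70%.

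Overstated residual effect follows only if the rule is programmed literally and baseline is complete or scaled; an unscaled baseline offsets part of it. The probabilities also assume a baseline of 20 and independent days. The consequence is confined to secondary and descriptive outputs of an open-label study whose primary objective is safety.

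**What to change.** In SAP 5.4.1, make the trigger the number of non-missing diary days x not being 30. State that this applies to every CGAP diary period that passes the compliance rule, including the CM baseline. Use one CM baseline window by reconciling the 30 days in SAP 5.4.1 with Visit 2 to Visit 3 in SAP 5.5.4; this is a smaller, separate point, but baseline is the denominator of every responder calculation. Confirm that EM baseline values taken from CGAN were scaled in the same way.

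No new data are needed. Follow-up already records "Number of diary days completed by the patient during Days 1-30 of the 60-day period since the last visit", with matching items for Days 31 to 60 and for treatment intervals, and SAP 5.5.7 already computes baseline compliance.

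The costs are modest. Scaling assumes that missed days resemble recorded ones. Sparse months become noisier, with a factor of up to 30/16 = 1.875. Integer counts can make responder classification conservative when one entry is missed. If any interim outputs were programmed literally they would need rerunning, since SAP 5.8.2 carries some interim analyses into the final report.

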5.4.2. Other Efficacy Measures

5.4.2.1. Patient Global Impression

The Patient Global Impression of Severity (PGI-S) will be collected at baseline and some post-baseline visits. In this single-item scale, patients rate the severity of their migraine condition on a scale ranging from “not at all ill”(coded as 1) to “extremely ill” (coded as 7).

The Patient Global Impression of Improvement (PGI-I) will be collected at some post-baseline visits during the treatment phase.

Change from baseline in PGI-S scores will be analyzed.

The PGI-I raw value will be analyzed with a mixed model repeated measures analysis with PGI-S baseline score.

PGI-S responder at each visit is defined as having a severity decrease from baseline of at least 2 points on the 7-point scale at the specific visit.

5.4.3. Quality of Life Questionnaires

5.4.3.1. Migraine Specific Quality of Life (MSQ) v2.1

Migraine Specific Quality of Life (MSQ) v2.1 consists of 14 questions. The questions measure the impact of migraine on health-related quality of life across 3 domains: 1) Role Function-Restrictive (7 questions), examines the degree to which performance of daily activities is limited by migraine; 2) Role Function-Preventive (4 questions), examines the degree to which performance of daily activities is prevented by migraine; 3) Emotional Function (3 questions), examines feelings of frustration and helplessness due to migraine.

Precoded item values and final item values for each MSQ item response are shown in [Table CGAP. 5.3](#). All item values range from 1 to 6. Final item value will be used as for analysis with higher score reflecting better quality of life.

Table CGAP. 5.3 Item Values for Migraine Specific Quality of Life (MSQ) Item

Response Categories	Precoded Item Value	Final Item Value
None of the time	1	6
A little bit of the time	2	5
Some of the time	3	4
A good bit of the time	4	3
Most of the time	5	2
All of the time	6	1

Questions 1 to 7 of the questionnaire will be grouped together as Role Function-Restrictive domain, questions 8 to 11 as Role Function-Preventive domain, and questions 12 to 14 as the Emotional Function domain.

The score of each domain will be calculated as the sum of the final item values of each question in that domain, using imputed scores where applicable.

When the number of missing items is fewer than or equal to 3 for the Role Function-Restrictive domain, the value of missing item(s) can be estimated using the average of the other completed items within the same domain. Similarly, when the number of missing items is fewer than or equal to 2 for the Role Function-Preventive, and fewer than or equal to 1 for the Emotional Function dimension, the value of missing item(s) can be estimated using the average of the other completed items within the same domain.

If the number of missing responses was more than half the questions in a domain, meaning that imputation of missing scores will not be done, then the raw score for that domain will not be calculated, hence set as missing.

The total score of all 3 domains will be calculated as the sum of raw scores of 3 domains. If any of the 3 domain scores is missing, then total score will be missing.

In addition, the raw scores of each domain and the total score will be transformed to a 0 to 100 scale using the following formulae:

- Role Function-Restrictive (range of 7 to 42):

$$\frac{(\text{raw score} - 7) \times 100}{35}$$

- Role Function-Preventive (range of 4 to 24):

$$\frac{(\text{raw score} - 4) \times 100}{20}$$

- Emotional Function(range of 3 to 18):

$$\frac{(\text{raw score} - 3) \times 100}{15}$$

- Total Score (range of 14 to 84):

$$\frac{(\text{raw total score} - 14) \times 100}{70}$$

The MSQ Role Function-Restrictive domain responder is defined as patients with the change from baseline subscore ≥ 25 for EM patients and ≥ 17.14 for CM patients.

5.4.3.2. MIDAS (Migraine Disability Assessment) Questionnaire

The Migraine Disability Assessment questionnaire (MIDAS) consists of 5 questions (Q1-Q5) and 2 additional questions (A and B). The questionnaire measures the impact that migraine headaches have on migraineurs' lives, including days of work or school missed, days with productivity at work or school reduced to half or more, days with household work missed, days with productivity in household work reduced to half or more, and days missed family/social/leisure activities. Each question is answered as a numeric number of days during the past 3 months of assessment, ranging from 0 to 90. The answers to all 5 questions will be added up to a total MIDAS score. No imputation is needed when calculating the total score, as patients are not allowed to send partial data.

The MIDAS responders are defined as patients with >50% improvement in the total MIDAS score.

The total MIDAS score, the raw score of each question, and the indicator of MIDAS responders will be used as analysis values.

5.4.3.3. HCRU (HealthCare Resource Utilization and Employment Status) Questionnaire and Employment Status

The Healthcare Resource Utilization (HCRU) will be solicited by study personnel while documenting patient responses. The HCRU consists of 3 questions;

1. Hospital emergency room visits since your last study visit (planned assessment visit) (YES/NO)
 - a. If yes, how many times did you go to a hospital emergency room?
 - b. How many of these times going to a hospital emergency room were related to your migraine headaches?
2. Overnight stays as a patient in a hospital since your last study visit (planned assessment visit) (YES/NO)
 - a. If yes, how many different times were you as a patient in a hospital overnight?
 - How many days total were you in the hospital for overnight stay?
 - b. How many of these times, as a patient in a hospital overnight, were related to your migraine headaches?
 - c. How many days total, as a patient in a hospital overnight, were related to your migraine headaches?
3. Any other visits with a healthcare professional that occurred since your last study visit (planned assessment visit) (YES/NO)
 - a. If yes, how many different times did you visit a healthcare professional?
 - b. How many of these times, visiting a healthcare professional, were related to your migraine headaches?

Regarding question 3, patients are specifically asked about the number of healthcare events that are related to migraine headaches, outside of visits associated with their participation in the clinical trial.

The baseline visit will include the same questions, however, with the frame of reference being over the last 6 months.

A question on employment status is also solicited, given the correlation and potential confounding with health outcomes measures. More specifically, one of the following statuses with additional information will be recorded.

- Working for pay
 - average number of hours worked (hours/week)
 - how long has the patient had this job? (number of weeks)
- Student
- Keeping house (full-time)
- Volunteer work
 - average number of hours volunteered (hours/week)
- Unemployed, *not* due to study disease disability
- Unemployed, due to study disease disability
- Retired
- Self-employed

There will be no imputation for missing values.

5.4.3.4. PSMQ-M (Patient Satisfaction with Medication Questionnaire-Modified) Questionnaire

The Patient Satisfaction with Medication Questionnaire-Modified (PSMQ-M) is a self-rated scale, which measures patients' levels of satisfaction with study medication (Kalali 1999). The scale has been modified for use in this study, assessing 3 items related to the clinical trial treatment over the past 4 weeks: satisfaction, preference, and side effects.

Satisfaction responses range from “very unsatisfied” to “very satisfied” with the current treatment (5 categories).

Preference compares the current study medication to previous medications, with responses from “much rather prefer my previous medication” to “much rather prefer the medication administered to me during the study” (5 categories).

The side effects responses range from “significantly less side-effects” to “significantly more side-effects” (5 categories).

Positive response for each item are defined as follows:

- Satisfaction : “Very satisfied” or “Somewhat Satisfied”
- Preference : “Much Prefer Study Medication” or “Prefer Study Medication”
- Side Effects: “Much Less Side Effects” or “Less Side Effects”

The PSMQ-M will be collected at Month 1, Month 6, Month 12, and Month 16.

